6.3 Conventions

All data listings, summaries, figures and statistical analyses will be generated using SAS version 9.4 or higher¹ unless otherwise noted.

Summaries will be presented by treatment group. Treatment group labels will be displayed as follows:

Engensis (N=XX)	Placebo (N=XX)	Overall (N=XX)
--------------------	-------------------	-------------------

Listings will be sorted in the following order treatment group, Participant, parameter unless otherwise stated. All data will be listed.

Continuous variables will be summarized by the number of non-missing observations, mean, median, standard deviation, and minimum and maximum. For all tabulations of changes from baseline data, the lower and upper 95% confidence limits for the mean for the individual treatments will be given.

Categorical variables will be summarized by presenting the frequency and percent. Percentages will be based on the number of non-missing observations or the participant population unless otherwise specified. For each variable, all categories will be shown. Zero frequencies (but not the percent) within a category will be presented.

6.3.1 Decimal Places

Decimal places for derived data described in section 6.2 will be determined by the scale of measurement unless otherwise stated. No decimal places will be displayed if the smallest calculated value is ≥ 100 ; 1 decimal place will be displayed when the smallest value is within the

QMD Ref: Worldwide-TMP-ST-005-7.0 Effective: 12Aug2019	Governing QMD: Worldwide-SOP-ST-001
Confidentiality Statement	

This document is the property of Worldwide Clinical Trials Inc. and may not be duplicated, copied, altered or removed from company without prior approval from Worldwide Quality Assurance or in compliance with Worldwide Standard Operating Procedures.

Worldwide Clinical Trials Controlled Quality Management Document			
 WORLDWIDE CLINICAL TRIALS	Sponsor:	Helixmith Co., Ltd.	
	Protocol Number:	VMALS-002-2b	
STATISTICAL ANALYSIS PLAN. PHASE 2-3-4			

interval (10, 100), with 10 being inclusive; 2 decimal places will be displayed when the smallest value is within (1, 10), with 1 being inclusive; and so on for even smaller scales of measurement.

Derived data where the result is known in advance will be an integer; for example day, month, year, number of days and total scores (for rating scales) will be presented with zero decimal places.

Means, medians and percentiles will be displayed to one more decimal place than the data, dispersion statistics (e.g. standard deviation) will have two more decimal places, and the minimum and maximum will be displayed to the same number of decimal places as reported in the raw data. Percentages will be displayed with one decimal place.

Rounding will be carried out according to the following rules: if the digits on the right start with 0, 1, 2, 3 or 4, then the rounding digit will remain unchanged, if the digits on the right begin with 5, 6, 7, 8 or 9, then the rounding digit will be increased by 1.

6.4 Subject Disposition

The following data will be tabulated: subjects completed the study, cases of withdrawal/discontinuation by primary reason will be tabulated for the Safety Analysis Population (Table 14.1.1.1). Participant visits will be presented in a separate table (Table 14.1.1.2).

The following data will be presented in a listing (Listing 16.2.1.1):

- Date of Informed Consent
- Original Consented Protocol Version
- Date of Discontinuation
- Primary reason for discontinuation
- Study completion (Yes/No)
- Date of last dose (from VMALS-002-2)
- Date of last visit

6.5 Protocol Deviations

A listing of protocol deviations will be provided. The listing will include participant number, protocol deviation description and deviation comments (Listing 16.2.1.2).

6.6 Baseline Comparability

QMD Ref: Worldwide-TMP-ST-005-7.0 Effective: 12Aug2019	Governing QMD: Worldwide-SOP-ST-001
Confidentiality Statement	

This document is the property of Worldwide Clinical Trials Inc. and may not be duplicated, copied, altered or removed from company without prior approval from Worldwide Quality Assurance or in compliance with Worldwide Standard Operating Procedures.

Worldwide Clinical Trials Controlled Quality Management Document			
 WORLDWIDE CLINICAL TRIALS	Sponsor:	Helixmith Co., Ltd.	
	Protocol Number:	VMALS-002-2b	
STATISTICAL ANALYSIS PLAN. PHASE 2-3-4			

Demographics and baseline characteristics will be presented for the Safety Analysis Population.

The comparability of treatment groups with respect to participant demographics and baseline characteristics will be assessed in a descriptive manner, but no formal statistical testing will be performed.

Standard continuous or categorical variable summaries will be presented by randomized treatment group for the following variables:

- Demographic and Baseline Characteristics collected at screening visit (Table 14.1.2.1)
 - Age
 - Gender
 - Child-bearing potential
 - Race
 - Ethnicity

Weight, height and BMI and their changes from baseline will be presented in a separate table (Table 14.1.2.2).

All demographic and baseline characteristics will be presented in a listing (Listing 16.2.4.1).

6.7 Medical History

Not applicable in this SAP.

6.8 Concomitant Medications

All collected medications will be considered as concomitant medications.

Concomitant medications will be presented for the Safety Analysis Population.

Concomitant medications will be coded using WHO Drug dictionary version March 2020 (or later) and summarized using Anatomic Therapeutic Chemical (ATC) Level 3.

Concomitant medications will be presented in a table by randomized treatment group (Table 14.3.8.1) and in a listing (Listing 16.2.4.2).

6.9 Exposure to Study Drug

Not applicable for this SAP.

6.10 Treatment Compliance

QMD Ref: Worldwide-TMP-ST-005-7.0 Effective: 12Aug2019	Governing QMD: Worldwide-SOP-ST-001
Confidentiality Statement	

This document is the property of Worldwide Clinical Trials Inc. and may not be duplicated, copied, altered or removed from company without prior approval from Worldwide Quality Assurance or in compliance with Worldwide Standard Operating Procedures.

Worldwide Clinical Trials Controlled Quality Management Document			
 WORLDWIDE CLINICAL TRIALS	Sponsor:	Helixmith Co., Ltd.	
Protocol Number:			VMALS-002-2b
STATISTICAL ANALYSIS PLAN. PHASE 2-3-4			

Not applicable for this SAP.

6.11 Efficacy Analyses

Not applicable for this SAP.

6.12 Pharmacokinetic Analyses

Not applicable for this SAP.

6.13 Pharmacodynamic Analyses

Not applicable for this SAP.

6.14 Safety Analyses

The safety analyses will be presented by the treatment received for the Safety Analysis Set.

6.14.1 Adverse Events

All study-related Adverse Events (AEs) will be collected starting after completion of the IC process at Screening to Day 0/randomization of the VMALS-002-2 study. Treatment-Emergent Adverse Events (TEAEs) and Treatment-Emergent Serious Adverse Events (TESAEs) will be collected after first injections of VMALS-002-2 study until the time that the Participant withdraws the IC of this study. All Serious Adverse Events (SAEs) will be collected from the completion of the IC process until the time that the Participant withdraws the IC of this study. Any SAE occurring after IC of VMALS-002-2 study and before the first injection should be recorded and reported only if associated with a VMALS-002-2 protocol-specified procedure. Any AEs reported during Screening of VMALS-002-2 study after completion of IC of VMALS-002-2 study will be collected and recorded separately from TEAEs reported on Day 0 and through the end of the study.

Medical occurrences that begin before the start of study intervention and not related to required study procedures, but after obtaining informed consent will be recorded on the Medical History/Current Medical Conditions section of the eCRF and not as AEs.

Adverse events with relationship equal to “Possibly related”, “Probably related” and “Definitely related” will be considered as adverse events related to study medication. If an AE has missing relationship it is assumed to be possibly related to the study drug for analysis purposes.

Adverse events with fatal outcome will be considered as fatal events. Maximum severity will be assumed for an AE with missing severity.

QMD Ref: Worldwide-TMP-ST-005-7.0 Effective: 12Aug2019	Governing QMD: Worldwide-SOP-ST-001
Confidentiality Statement	

This document is the property of Worldwide Clinical Trials Inc. and may not be duplicated, copied, altered or removed from company without prior approval from Worldwide Quality Assurance or in compliance with Worldwide Standard Operating Procedures.

Worldwide Clinical Trials Controlled Quality Management Document			
 WORLDWIDE CLINICAL TRIALS	Sponsor:	Helixmith Co., Ltd.	
Protocol Number:			VMALS-002-2b
STATISTICAL ANALYSIS PLAN. PHASE 2-3-4			

AEs will be coded using Medical Dictionary of Regulated Activities (MedDRA, version 23.0, or later) by System Organ Class (SOC) and preferred term (PT).

In this study the adverse events (AEs) will be presented from collected since Screening visit of VMALS-002-2 study. AEs that registered as not treatment emergent (not TEAEs) will be presented in a separate listing and will not be tabulated. TEAEs will be tabulated in similar manner as two sets: TEAEs started at date of signing of IC for this study or later and all TEAEs collected during both studies. All AEs from both studies will be united for presenting in listings.

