8.3.4.2. Other Medical Problems in ALS Patients

Several medical problems are frequently observed in patients with ALS that should be considered AESIs. These medical problems are listed below.

- Pulmonary Medical Problems: Because patients with ALS are at an increased risk to develop pulmonary medial problems such as aspiration of food or liquids, pneumonia, and respiratory arrest, all events of this type that occur during the study will be considered AESIs.

- **Progressive Muscle Weakness:** Because some patients with ALS may develop rapidly progressive muscle weakness that results in loss of ability to care for self, decubitus ulcers, or weight loss due to impaired deglutition; all events of this type that occur during the study will be considered AESIs.
- **Bulbar Disease:** Participants may develop bulbar disease or worsening on bulbar disease during the study, manifested as challenges with dysarthria, facial weakness, impaired tongue pulsion or palate elevation, and impaired mastication and swallowing; all of these types of events that occur during the study will be considered AESIs.

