8.3.5. Follow-up of TEAEs, TESAEs, and AESIs

After the initial TEAE or TESAE report, the Investigator is required to proactively follow each Participant at subsequent Visits/contacts. All TEAEs, TESAEs, and AESIs (see Section 8.3.4) will be followed until resolution, stabilization, the event is otherwise explained, or the Participant is lost to follow-up (as defined in Section 10.2.3, Appendix 2).

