10.2.3. Definition of TESAE

Treatment-Emergent Serious Adverse Event is defined as:

- A serious event that emerges during treatment, having been absent at pretreatment, or worsens relative to the pretreatment state, as defined in the E9 Guidance.
- The TESAE is not related to causality / drug relatedness. It may or may not be related to the drug but is considered a TESAE due to its appearance at or after the treatment has been administered.

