- Alternative causes, such as underlying disease(s), concomitant therapy, and other risk factors, as well as the temporal relationship of the event to study intervention administration will be considered and investigated.
- The Investigator will also consult the IB and/or Product Information, for marketed products, in his/her assessment.
- For each TEAE/TESAE, the Investigator **must** document in the medical notes that he/she has reviewed the TEAE/TESAE and has provided an assessment of causality.
- Situations may arise in which a TESAE has occurred, and the Investigator has minimal information to include in the initial report to the Sponsor or designee. However, the Investigator must always assess causality for every event before the initial transmission of the TESAE data to the Sponsor or designee. Death or hospitalization are not to be specified as a TESAE; these are criteria to determine seriousness.
- The Investigator may change his/her opinion of causality in light of follow-up information and send an TESAE follow-up report with the updated causality assessment.
- The causality assessment is one of the criteria used when determining regulatory reporting requirements.

Follow-up of TEAEs and TESAEs

- The Investigator is obligated to perform or arrange for the conduct of supplemental measurements and/or evaluations as medically indicated or as requested by the Sponsor or designee to elucidate the nature and/or causality of the TEAE or TESAE as fully as possible. This may include additional laboratory tests or investigations, histopathological examinations, or consultation with other health care professionals. New or updated information will be recorded in the originally completed eCRF.
- The Investigator will submit any updated TESAE data to the Sponsor or designee within 24 hours of receipt of the information.

10.2.5. Reporting of TESAEs**TESAE Reporting to the Sponsor or Designee via an Electronic Data Collection Tool**

- The primary mechanism for reporting an TESAE to the Sponsor or designee will be the eCRF.
- The Site will enter the TESAE data into the electronic system as soon as it becomes available.
- After the study is completed at a given Site, the electronic data collection tool will be taken off-line to prevent the entry of new data or changes to existing data.

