6.14.1.1 Treatment Emergent Adverse Event (TEAE) Definition

- A TEAE is any untoward medical occurrence associated with the use of an investigational product or study procedure in a clinical study Participant, whether or not considered related to the study intervention.
- NOTE: A TEAE can therefore be any unfavorable and unintended sign (including an abnormal laboratory finding), symptom, or disease (new or exacerbated) temporally associated with the use of study intervention or procedure.
- An event that emerges during treatment, having been absent at pretreatment, or worsens relative to the pretreatment state, as defined in the E9 Guidance.
- The TEAE is not related to causality / drug relatedness. It may or may not be related to the drug but is considered a TEAE due to its appearance at or after the treatment has been administered.

Events Meeting the TEAE Definition

- Any abnormal laboratory test results (hematology, or clinical chemistry) or other safety assessments (e.g., ECG, radiological scans, vital signs measurements), including those that worsen from Baseline, considered clinically significant in the medical and scientific judgment of the investigator (i.e., not related to progression of underlying disease).
- Exacerbation of a chronic or intermittent pre-existing condition including either an increase in frequency and/or intensity of the condition.
- New conditions detected or diagnosed after study intervention administration even though it may have been present before the start of the study.
- Signs, symptoms, or the clinical sequelae of a suspected drug-drug interaction.
- Signs, symptoms, or the clinical sequelae of a suspected overdose of either study intervention or a concomitant medication. Overdose per se will not be reported as an TEAE/TESAE unless

QMD Ref: Worldwide-TMP-ST-005-7.0 Effective: 12Aug2019	Governing QMD: Worldwide-SOP-ST-001
Confidentiality Statement	

This document is the property of Worldwide Clinical Trials Inc. and may not be duplicated, copied, altered or removed from company without prior approval from Worldwide Quality Assurance or in compliance with Worldwide Standard Operating Procedures.

Worldwide Clinical Trials Controlled Quality Management Document			
 WORLDWIDE CLINICAL TRIALS	Sponsor:	Helixmith Co., Ltd.	
	Protocol Number:	VMALS-002-2b	
STATISTICAL ANALYSIS PLAN. PHASE 2-3-4			

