6.14.1.4 Outputs planned for Adverse Events

TEAEs with start date and time before date and time of the Informed Consent for VMALS002-2B will be presented in a separate listing and will not be tabulated.

The following tables will be presented:

- Summary of TEAEs (Table 14.3.1.1)
- TEAEs by System Organ Class and Preferred Term (Table 14.3.1.2)
- TESAEs by System Organ Class and Preferred Term (Table 14.3.1.3)
- TEAEs by System Organ Class and Preferred Term and Maximum Severity (Table 14.3.1.4)

QMD Ref: Worldwide-TMP-ST-005-7.0 Effective: 12Aug2019	Governing QMD: Worldwide-SOP-ST-001
Confidentiality Statement	

This document is the property of Worldwide Clinical Trials Inc. and may not be duplicated, copied, altered or removed from company without prior approval from Worldwide Quality Assurance or in compliance with Worldwide Standard Operating Procedures.

Worldwide Clinical Trials Controlled Quality Management Document			
 WORLDWIDE CLINICAL TRIALS	Sponsor:	Helixmith Co., Ltd.	
	Protocol Number:	VMALS-002-2b	
STATISTICAL ANALYSIS PLAN. PHASE 2-3-4			

- TEAEs by System Organ Class and Preferred Term and Maximum Relationship (Table 14.3.1.5)
- TESAEs by System Organ Class and Preferred Term and Maximum Severity (Table 14.3.1.6)
- TESAEs by System Organ Class and Preferred Term and Maximum Relationship (Table 14.3.1.7)
- Incidence of Clinically Significant Laboratory Values (Table 14.3.1.8)
- AESIs by System Organ Class and Preferred Term (Table 14.3.1.9)

The following listings will be provided:

- All TEAEs (Listing 16.2.7.1)
- AESIs (Listing 16.2.7.2)
- TESAEs (Listing 16.2.7.3)
- TEAEs leading to study discontinuation (Listing 16.2.7.4)
- TEAEs related to study medication (Listing 16.2.7.5)
- TESAEs leading to death (Listing 16.2.7.6)
- AEs that registered as not TEAEs (Listing 16.2.7.7)

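### The extension TEAE set is defined by start date alone, so core-study events that become serious or fatal after extension consent are absent from its tables, and SAP 6.14.1 and 6.14.1.4 disagree on whether they are tabulated anywhere.

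*SAP*

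**What the plan says.** SAP 6.14.1 tabulates TEAEs twice, as "TEAEs started at date of signing of IC for this study or later and all TEAEs collected during both studies". The first of these is the extension set, and its only entry condition is the start date. SAP 6.14.1.4, which lists the outputs, says that "TEAEs with start date and time before date and time of the Informed Consent for VMALS002-2B will be presented in a separate listing" and adds that they are left out of the tables.

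Protocol 8.3.5 says that open events "will be followed until resolution, stabilization, the event is otherwise explained, or the Participant is lost to follow-up". Protocol 10.2.4, on follow-up, says: "New or updated information will be recorded in the originally completed eCRF". The same section says that death and hospital admission are grounds for calling an event serious and may not themselves be reported as the TESAE.

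The definitions do treat worsening as an event. Protocol 10.2.3 defines a TESAE as "A serious event that emerges during treatment, having been absent at pretreatment, or worsens relative to the pretreatment state", and SAP 6.14.1.1 covers an event that "worsens relative to the pretreatment state, as defined in the E9 Guidance". The reference is the state before the first injection, not the state at entry to the extension. SAP 6.14.1.1 also accepts as a TEAE: "Exacerbation of a chronic or intermittent pre-existing condition including either an increase in frequency and/or intensity of the condition". Among the AESIs, Protocol 8.3.4.2 notes that "Participants may develop bulbar disease or worsening on bulbar disease during the study".

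The primary endpoints (Protocol 9.3.1, SAP 3.1) are incidences, summarised without formal testing. Neither document says which of the two TEAE sets answers the primary objective.

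**The concern.** The extension exists to describe long-term safety after injections given only in the core study. Some late serious events will be the later course of something that began before the extension: a swallowing problem that ends in aspiration, or a cancer diagnosed in the core study that proves fatal. Protocol 2.3.1 names long-term follow-up in the extension as the mitigation for exactly those cancers.

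If such an event keeps its core-study start date, the extension tables do not show that it became serious or fatal in the extension period. The extension incidence of TESAEs and AESIs is then too low, and a reader of those tables alone would not know it. The problem does not depend on missing dates or on when consent is signed. It arises with complete dates and with consent exactly on Day 180.

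**Working it through.** The documents give no figure to reproduce. There is no power calculation, and 18 is a ceiling set by core-study enrolment (SAP 4). The check is a trace through the rules, followed by a scale calculation.

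**Trace.** Take a hypothetical TEAE that starts on Day 150, is still open at consent on Day 180, and leads to admission or death on Day 290.

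1. It was open at consent, so Protocol 8.3.5 carries it into the extension.
2. The admission or death cannot be an event of its own (Protocol 10.2.4), so it becomes an attribute of the Day 150 event.
3. If the update goes onto the existing record (Protocol 10.2.4), the start date remains Day 150.
4. Day 150 is before consent, so the event fails the entry condition of the extension set (SAP 6.14.1).
5. No other rule assigns a change in severity, seriousness or outcome to a study period.

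| Output | Existing record updated | New record opened for the change |
|---|---|---|
| Extension-set tables (SAP 6.14.1) | not counted | counted |
| Both-studies tables (SAP 6.14.1) | counted, but the change is not placed in the extension | counted |
| AE tables if SAP 6.14.1.4 is followed literally | not counted | counted |
| Listings (SAP 6.14.1, 6.14.1.4) | shown | shown |
| Combined Kaplan-Meier analysis (SAP 6.15.7) | death included | death included |

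The right-hand column is realistic mainly for a worsening, where the exacerbation clause gives a site a reason to open a new record. For an event that only becomes serious or fatal, the rule on death and hospitalisation points to the left-hand column.

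**Weight of one participant.** The change in incidence is 100 × 1/n, provided that the participant has no other qualifying event in the extension set.

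- Overall, n = 18 (SAP 4): 100/18 = 5.6 points.
- By arm, 9:9 split (assumed): 100/9 = 11.1 points.
- By arm, 12:6 split (assumed): 100/12 = 8.3 points for Engensis and 100/6 = 16.7 points for Placebo.
- With 12 enrolled (assumed): 100/6 = 16.7 points at 6:6, or 100/8 = 12.5 and 100/4 = 25.0 points at 8:4.

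**Chance that it happens at all.** If each of 18 participants has probability q of such an event, the chance of at least one is 1 − (1 − q)^18. For assumed q of 5%, 10% and 20% this gives 60%, 85% and 98%. The documents supply no value for q.

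**Where it would show.** In the earlier 18-participant ALS study (Protocol 1.1), 17 of 18 (94.4%) had an adverse event and 3 of 18 (3/18 = 16.7%) had a serious one over 9 months. If the extension is similar, overall TEAE incidence would hardly move, because almost everyone qualifies anyway. TESAE incidence, and the rows by preferred term, would.

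**The case against.** The strongest reply is that the sentence defining the extension set also provides the remedy, because the both-studies set counts every one of these events with its updated seriousness. A reader might infer that they are missing from the tables that answer the primary objective. The documents do not support that. Neither document makes the extension set primary, and since all injections were given in the core study, a cumulative set from first injection is arguably the closer match to long-term safety of the injections. What remains is that the cumulative set cannot show when the change occurred, and that SAP 6.14.1.4, taken literally, removes it from the tables. That sentence may have been meant for the extension set only, but it is not so limited.

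Second, the eCRF sentence in Protocol 10.2.4 closes a paragraph about supplementary tests and consultations. It does not expressly order a clinical worsening onto the old record. The exacerbation clause, the AESI wording on bulbar worsening and the statement that complications during hospitalisation are AEs (Protocol 10.2.2) all allow a new record, and eCRF guidelines outside these documents may settle it. This stands for worsening, so it would go too far to say that every worsening is lost. It does less for later seriousness or death.

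Third, expected ALS progression is not a TEAE unless more severe than expected, and death from progression cannot be a TESAE (Protocol 10.2.1, 10.2.2). Malignant cancers would usually be serious from onset (Protocol 10.2.2), so for them the omission is mainly of a fatal outcome. This reduces the number of affected events without removing them.

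Fourth, classification by onset date applies equally to both arms, and the analysis is descriptive. A reader might infer a bias between Engensis and Placebo. That would need unequal numbers of core-study events still open at consent, and nothing in the documents shows it.

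**Conclusion.** The concern holds for the extension set. Under the written rules, a core-study TEAE that becomes serious or fatal after extension consent does not appear in the extension-set TEAE, TESAE or AESI tables. The same is true of one that worsens, if the site updates the existing record. The both-studies set contains these events but cannot attribute the change to the extension. SAP 6.14.1 and 6.14.1.4 contradict each other on whether that set is tabulated. If 6.14.1.4 prevails, the events are in no AE table, only in listings, with deaths also in the exploratory Kaplan-Meier analysis.

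The extension incidence can only be understated by this, never overstated. One omitted participant is 5.6 points overall at 18 enrolled, and more if fewer enrol. By arm it is 11.1 points at an assumed 9:9 split, or 8.3 or 16.7 points at an assumed 12:6 split. Each figure assumes that the participant has no other qualifying extension event. The number of such participants cannot be estimated from the documents. The point should be corrected before database lock, but it does not invalidate the trial.

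**What to change.** 1. Reconcile SAP 6.14.1 with 6.14.1.4 so that the both-studies set is tabulated. Limit the exclusion of TEAEs that began before consent to the extension set, subject to item 2.
2. Define the extension set as TEAEs, TESAEs and AESIs that start, increase in severity, become serious or become fatal on or after extension consent, counted by participant.
3. Collect the date of worsening and the date of seriousness for events open at consent, either on the existing record or on a linked new one. Put this in an eCRF completion instruction with matching wording in Protocol 10.2.4.
4. State which of the two sets is primary.

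The cost is a revision of the SAP, an eCRF instruction and a minor protocol wording change. One medical course may produce two linked records, which is why counting should be by participant, and extension incidences will be slightly higher than under the start-date rule.

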3. OBJECTIVES AND ENDPOINTS

Objectives and endpoints for this extension study are presented in the following table. Note that there will be no Engensis or Placebo treatments in VMALS-002-2b. Therefore, the comparisons of Engensis to Placebo for long-term safety in VMALS-002-2b are based on the randomization of Participants and the treatments they received in VMALS-002-2 (Engensis or Placebo).

Objectives	Endpoints
Primary	

 To evaluate the long-term safety of intramuscular (IM) injections of Engensis in Participants with Amyotrophic Lateral Sclerosis (ALS) 	
 Incidence of treatment-emergent adverse events (TEAEs), treatment-emergent serious adverse events (TESAEs), and adverse events of special interest (AESIs) for Engensis compared to Placebo Incidence of clinically significant laboratory values for Engensis compared to Placebo
Exploratory	

 To evaluate changes in muscle function following Engensis injections in ALS Participants 	
 Change from Baseline (Study VMALS-002-2 Day 0) in total mean Revised Amyotrophic Lateral Sclerosis Function Rating (ALSFRS-R) scores at Day 365 for Engensis compared to Placebo Change from Baseline (Study VMALS-002-2 Day 0) in ALSFRS-R subscores for Fine and Gross Motor Functions (sum of scores for items 4 to 9) and for Bulbar Function (sum of scores for items 1 to 3) at Day 365 for Engensis compared to Placebo Changes in the slope of the total ALSFRS-R score over time for Engensis compared to Placebo

Objectives	Endpoints

 To evaluate muscle strength changes following Engensis injections in ALS Participants 	
 Change from Baseline (Study VMALS-002-2 Day 0) in muscle strength assessed bilaterally by Handheld Dynamometry (HHD) in muscles in the upper and lower extremities at Day 365 for Engensis compared to Placebo

 To determine whether IM administration of Engensis has effects on respiratory function in ALS Participants 	
 Change from Baseline (Study VMALS-002-2 Day 0) in Slow Vital Capacity (SVC) at Day 365 for Engensis compared to Placebo Time to tracheostomy for Engensis

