5. STUDY POPULATION

Participants who complete the Day 180 Visit in VMALS-002-2 are eligible to enroll in this extension study, VMALS-002-2b.

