5.1. Number of Participants

The number of Participants to be enrolled in this extension study depends upon the number of Participants who complete the Day 180 Visit in VMALS-002-2 and provide written informed consent for this extension protocol (prior to, during, or after their Day 180 Visit in the VMALS-002-2 study).

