6.1 Analysis Sets

6.1.1 Safety Analysis Population

The safety analysis population will contain all Participants who sign the Informed Consent of the VMALS-002-2b study. Participants will be grouped according to their actual treatment received in VMALS-002-2 study.

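### The planned TEAE tables covering both studies are restricted to extension consent signers, so core participants whose TEAE ended participation before Day 180 are, with one narrow exception, left out

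*SAP*

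**What the plan says.** The extension is open to a selected group. Protocol 5 states: "Participants who complete the Day 180 Visit in VMALS-002-2 are eligible to enroll in this extension study, VMALS-002-2b". Protocol 5.1 also requires written consent, which may be given "prior to, during, or after their Day 180 Visit in the VMALS-002-2 study".

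The SAP defines one analysis population. SAP 6.1.1: "The safety analysis population will contain all Participants who sign the Informed Consent of the VMALS-002-2b study". SAP 6.14 then applies it: "The safety analyses will be presented by the treatment received for the Safety Analysis Set". Protocol 9.2 and 9.3.1 likewise put every safety analysis on the Safety Population, which they define as those who enroll in the extension.

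SAP 6.14.1 says TEAEs will be tabulated in two sets: "TEAEs started at date of signing of IC for this study or later and all TEAEs collected during both studies". No wider population is named for the second set.

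SAP 6.14.1.4 says something different. TEAEs that start before the extension consent go to a separate listing and stay out of the tables. It then gives one series of AE tables, 14.3.1.1 to 14.3.1.9. The list of tables in SAP section 11 is not legible in the public copy and cannot settle the matter.

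SAP 6.2.3, 6.15.6 and 6.15.7 time tracheostomy and death from the first core injection and combine the data of the two studies. They name no separate population either.

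**The concern.** A table presented as covering both studies will be read as the cumulative safety record since first injection. Built on the extension consent set, it covers the core treatment period only in people who reached the end of it and agreed to continue. The events most likely to be missing are those that stopped participation: fatal TEAEs and TEAEs leading to withdrawal. If these were unevenly spread between Engensis and Placebo, the cumulative comparison would be distorted, and the reader could not see it. The disposition table also begins with the extension set (SAP 6.4: "cases of withdrawal/discontinuation by primary reason will be tabulated for the Safety Analysis Population"), so no planned table shows how many treated participants per arm did not enter, or why.

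**Working it through.** The plan gives no incidence, power or precision figure to reproduce. The check has two parts: trace the definitions, then illustrate the size.

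**Tracing the definitions**

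| Step | Source | Consequence |
|---|---|---|
| Entry needs core Day 180 completed, plus consent | Protocol 5, 5.1 | Both conditions arise after randomisation |
| Population = signers of the extension consent | SAP 6.1.1 | No all-treated core set exists |
| Safety analyses use that set | SAP 6.14; Protocol 9.3.1 | Applies to every TEAE table |
| Second TEAE set spans both studies | SAP 6.14.1 | Event window opens at first core injection |
| TEAEs before extension consent only listed | SAP 6.14.1.4 | Conflicts with the row above |

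Under SAP 6.14.1 the cumulative tables exist but omit early leavers. Under SAP 6.14.1.4 core-period TEAEs are not tabulated for anyone. Neither reading shows the missing events in a table.

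**Size**

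Inputs: at most 18 participants (Protocol 1.1, SAP 4). The allocation ratio and core losses are not given, so the values below are assumptions. Let *n* be the number treated in an arm, *x* the entrants with a TESAE, and *k* the participants who left the core study with a TESAE and did not enter.

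- Shown in the table: x / (n − k)
- All treated: (x + k) / n

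With n = 9 and x = 1:

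| k | Shown | All treated | Gap (points) | Gap per case |
|---|---|---|---|---|
| 0 | 1/9 = 11.1% | 1/9 = 11.1% | 0 | – |
| 1 | 1/8 = 12.5% | 2/9 = 22.2% | 9.7 | 9.7 |
| 2 | 1/7 = 14.3% | 3/9 = 33.3% | 19.0 | 9.5 |
| 3 | 1/6 = 16.7% | 4/9 = 44.4% | 27.8 | 9.3 |

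With a 12:6 split, x = 1 and k = 1:

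- Larger arm: 1/11 = 9.1% against 2/12 = 16.7%, a gap of 7.6 points.
- Smaller arm: 1/5 = 20.0% against 2/6 = 33.3%, a gap of 13.3 points.

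**Could there be any early leavers?** If each of 18 participants has probability *p* of loss before Day 180 for any reason, the chance of at least one loss is 1 − (1 − p)^18. This is 30.5% at p = 2%, 60.3% at 5%, 85.0% at 10% and 98.2% at 20%. Only losses accompanied by a TEAE matter for the TEAE tables, so these figures are upper guides.

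**The case against.** Several points on the other side stand.

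- **The target may not exist.** If SAP 6.14.1.4 governs, there are no both-studies tables to correct. This makes reconciling the two passages the first step.
- **The primary endpoint rests mainly elsewhere.** The objective is long-term safety, and Protocol 8.3.1 collects events from the extension consent onward. The extension-period tables serve that purpose and are unaffected. Protocol 9.3.1 asks for no cumulative table and plans no formal testing.
- **The exclusion is not absolute.** Consent may precede Day 180 and the SAP set is defined by signature. An early signer who then died or withdrew would be counted under SAP 6.1.1.
- **Many ALS deaths are outside the issue.** Expected progression is not a TEAE (Protocol 10.2.1), and death from progression cannot be a TESAE (Protocol 10.2.2). Those deaths would be absent from TESAE tables on any denominator.
- **Few losses are plausible.** The one retention figure in the documents is from the earlier open-label ALS study (Protocol 2.2.6.1), where 17 of 18 completed nine months and one died. It is a different study, but it makes two or three losses in one arm look extreme.
- **The core study's own report may show these events.** It is not among the documents. It would not correct a cumulative table whose title suggests completeness.

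A reader might also infer that the protocol claims an intact randomised comparison, from Protocol 3: "Therefore, the comparisons of Engensis to Placebo for long-term safety in VMALS-002-2b are based on the randomization of Participants". The sentence continues by naming the treatments received in the core study, and it follows a statement that no treatment is given in the extension. It reads most naturally as explaining where the group labels come from, so it does not support that inference.

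**Conclusion.** The gap is real but limited to the cumulative tables. As SAP 6.14.1, 6.14 and 6.1.1 stand together, a core participant whose TEAE caused death or withdrawal before Day 180 contributes to neither numerator nor denominator, apart from anyone who had already signed the extension consent. SAP 6.14.1.4 leaves it unclear whether those tables will be produced at all.

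One excluded TESAE case lowers the arm's shown incidence by about 9 to 10 points if there were 9 per arm and one TESAE among entrants. With a 12:6 split it is about 8 points in the larger arm and 13 in the smaller. These are illustrations.

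A reader might infer that the plan makes Engensis look safer than it is. The documents do not support this. Core losses by arm are not given, so neither the size nor the direction of any bias between arms can be stated, and there may have been no relevant losses.

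The combined time-to-death and time-to-tracheostomy curves have the same weakness if run on this set. Apart from early signers, nobody in it could have died before Day 180, yet the clock starts at first injection. Here deaths from ALS progression do count.

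**What to change.** 1. Reconcile SAP 6.14.1 with SAP 6.14.1.4: state whether TEAEs from before the extension consent are tabulated.
2. Keep the extension consent set for the extension-period TEAE tables.
3. If both-studies TEAE, TESAE and AESI tables are produced, define a second population of all participants who received at least one VMALS-002-2 injection, grouped by treatment received, and use it for those tables.
4. If that is not possible, title the tables as extension entrants only. Show beside them, by arm, the number treated in the core study who did not enter the extension, with the reason.
5. Apply the same population to the time-to-death and time-to-tracheostomy analyses in SAP 6.15.6 and 6.15.7.

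The cost is SAP wording, a second denominator in the AE outputs, and access to core-study data for people who did not enter. The documents do not say that those data are held with the extension database. Option 4 needs only core-study counts and reasons for non-entry. A fuller disposition table starting from randomisation would help but comes second to settling the population.
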